14.5. Subject Data Protection

In accordance with the Health Information Portability and Accountability Act (HIPAA), subjects who have provided written informed consent must also sign a subject authorization to release medical information to the study Sponsor and allow a regulatory authority, or Institutional Review Board access to subject's medical information relevant to the study.

14.6. Data and Safety Monitoring/Auditing

In addition to adverse event monitoring and clinical oversight by the Study Chair, site principal investigator and co-investigators, quality assurance of the study will be performed by the UCSD Moores Cancer Center Clinical Trials Office internal monitor. Monitoring intervals will be dependent upon risk-based assessments.

This study will also use the UCSD Moores Cancer Center Data Safety and Monitoring Board (DSMB) to provide oversight in the event that this treatment approach leads to unforeseen toxicities. Data from this study will be reported annually and will include:

- 1) the protocol title, IRB protocol number, and the activation date of the study.
- 2) the number of patients enrolled to date.
- 3) the date and site of patients' enrollment.
- 4) a summary of all adverse events regardless of grade and attribution.
- 5) a response evaluation for evaluable patients when available.
- 6) a summary of any recent literature that may affect the ethics of the study.

14.7. Adherence to the Protocol

Except for an emergency situation in which proper care for the protection, safety, and well-being of the study patient requires alternative treatment, investigators are required to conduct their research according to the plans reviewed and approved by the IRB.

14.7.1. Emergency Modifications

Investigators may implement a deviation from, or a change of, the protocol to eliminate apparent immediate hazards/risks to trial subjects without prior IRB approval. Any such emergency modification implemented must be noted and reported to the IRB along the lines of a protocol deviation or violation, depending on the nature of the modification.

14.7.2. Protocol Violations

Any unplanned variance from an IRB approved protocol is considered a violation and must be reported to the IRB in a timely fashion. For the UCSD IRB:

- A. Major violations must be reported to the IRB within 10 working days of awareness of the violation.

Major violations include:

- Instances that have harmed or increased the risk of harm to one or more research participants.
- Instances that have damaged the scientific integrity of the data collected for the study.
- Results from willful or knowing misconduct on the part of the investigator(s).
- Demonstrates serious or continuing noncompliance with federal regulations, State laws, or University policies.

- B. Minor violations may be reported to the IRB at the time of the continuing review.

Minor violations have no substantive effect on the risks to participants or on the scientific integrity of the research plan or the value of the data collected.

14.8. Amendments to the Protocol

Should amendments to the protocol be required, the amendments will be originated and documented by the Study Chair. It should also be noted that when an amendment to the protocol substantially alters the study design or the potential risk to the patient, a revised consent form might be required.

Per the IST Agreement, any amendments to the Protocol or Informed Consent Form must be sent to Pharmacyclics for review and approval prior to submission to the IRB.

The written amendment, and if required the amended consent form, must be sent to the IRBs at each site and submitted to the FDA by the Study Chair for approval prior to implementation.

14.9. Record Retention

Study documentation includes all Case Report Forms, data correction forms or queries, source documents, Sponsor-Investigator correspondence, monitoring logs/letters, and regulatory documents (e.g., protocol and amendments, IRB correspondence and approval, signed patient consent forms).

Source documents include all recordings of observations or notations of clinical activities and all reports and records necessary for the evaluation and reconstruction of the clinical research study.

Government agency regulations and directives require that the study investigator must retain all study documentation pertaining to the conduct of a clinical trial. In the case of a study with a drug seeking regulatory approval and marketing, these documents shall be retained for at least two years after the last approval of marketing application in an International Conference on Harmonization (ICH) region. In all other cases, study documents should be kept on file until three years after the completion and final study report of this investigational study.

14.10. Obligations of Investigators

The Principal Investigator is responsible for the conduct of the clinical trial at the site in accordance with Title 21 of the Code of Federal Regulations and/or the Declaration of Helsinki. The Principal Investigator is responsible for personally overseeing the treatment of all study patients. The Principal Investigator must assure that all study site personnel, including sub-investigators and other study staff members, adhere to the study protocol and all FDA/GCP/NCI regulations and guidelines regarding clinical trials both during and after study completion.

The Principal Investigator at each institution or site will be responsible for assuring that all the required data will be collected and entered onto the Case Report Forms. Periodically, monitoring visits will be conducted and the Principal Investigator will provide access to his/her original records to permit verification of proper entry of data. At the completion of the study, all case report forms will be reviewed by the Principal Investigator and will require his/her final signature to verify the accuracy of the data.

16. APPENDICES

CONFIDENTIAL

Appendix 1. Schedule of Assessments

SCHEDULE OF ASSESSMENTS

| Procedure | Screen/ Baseline (≤ 28 days, unless otherwise noted) | Treatment Cycles (4-week cycles) | | | | | | | | | | | | | | | | | | | | End of Treatment (within 28 days after last dose) | Follow-up (q2 months (± 14 days) from EOT) | |
|---------------------------------------|---|----------------------------------|---|---|----|----|-----------------------|---|----|----|-----------------------|---|----|----|-----------------------|---|----|----|--|---|----|---|---|----|
| | | Cycle 1 (± 3 days) | | | | | Cycle 2 (± 3 days) | | | | Cycle 3 (± 3 days) | | | | Cycle 4 (± 3 days) | | | | Each Additional Cycle (± 3 days) | | | | | |
| | | -7 | 1 | 8 | 15 | 22 | 1 | 8 | 15 | 22 | 1 | 8 | 15 | 22 | 1 | 8 | 15 | 22 | 1 | 8 | 15 | | | 22 |
| Informed Consent | X | | | | | | | | | | | | | | | | | | | | | | | |
| Eligibility | X | | | | | | | | | | | | | | | | | | | | | | | |
| Medical History | X | | | | | | | | | | | | | | | | | | | | | | | |
| HPV or p16 status ¹ | | | | | | | | | | | | | | | | | | | | | | | | |
| Demographics | X | | | | | | | | | | | | | | | | | | | | | | | |
| Concomitant Medications Assessment | X | | | X | | | X | | | | X | | | | X | | | | X | | | | X | |
| Adverse Event Assessment | X | | | X | | | X | | | | X | | | | X | | | | X | | | | X | |
| Physical Exam ² | X | | | X | | | X | | | | X | | | | X | | | | X | | | | X | |
| Vital Signs & Height | X | | | X | | | X | | | | X | | | | X | | | | X | | | | X | |
| ECOG | X | | | X | | | X | | | | X | | | | X | | | | X | | | | X | |
| CBC with Diff ³ | X | X | | X | | | X | | | | X | | | | X | | | | X | | | | X | |
| CMP and magnesium ⁴ | X | X | | X | x | | X | | x | | X | | x | | X | | x | | X | | x | | X | |
| PT/INR, aPTT | X | X | | | | | | | | | | | | | | | | | | | | | | |
| Pregnancy test ⁵ | Within 72 hours | | | | | | | | | | | | | | | | | | | | | | | |
| HIV | X | | | | | | | | | | | | | | | | | | | | | | | |
| HEP B & C | X | | | | | | | | | | | | | | | | | | | | | | | |
| T4 and TSH | X | | | | | | X | | | | X | | | | X | | | | X | | | | | |
| ECG | X | | | | | | | | | | | | | | | | | | | | | | | |
| Tumor tissue collection ⁶ | Within 42 days | | | | | | X ¹ 0 | | | | | | | | | | | | | | | | | |

[illegible]

Cycles are 28 days in length, with the exception of cycle 1, which is 35 days long due to start of ibrutinib 7 days prior to second drug.

1. By standard institutional practices. Required only for oropharyngeal and unknown primary tumors
2. Full physical exam at baseline; targeted physical exam at other time points.
3. CBC with Diff: Complete blood count with differential.
4. CMP: Comprehensive metabolic panel (bicarbonate, calcium, chloride, creatinine, glucose, potassium, sodium BUN, albumin, bilirubin total, alkaline phosphatase, total protein, ALT, AST).
5. Pregnancy test for females of child-bearing potential only. Should be obtained with 72 hours of starting therapy and again as indicated
6. Newly obtained tumor tissue collection should be performed when feasible. Otherwise, an archived tumor specimen is adequate.
7. Blood for correlative studies should be collected at the same time blood is drawn for CBC and CMP if possible. 30 ml blood to be collected prior to initiation of study treatment and on cycle 2 day 1 (± 7 days).
8. Imaging for radiographic disease assessment will be performed every 8 weeks (every 2 cycles) following treatment initiation (± 7 days). The same imaging modality should be used throughout the study when feasible. For patients who are clinically stable, a repeat scan will be required 4 weeks (± 7 days) after initial radiographic findings of disease progression as a confirmatory assessment. For CT or MRI, neck and chest should be evaluated; abdomen/pelvis as indicated. If a PET/CT is utilized, CT must be diagnostic quality.
9. Ibrutinib administration will begin 7 days before the start of the second agent and is taken orally on a daily basis.
10. +/- 7 days

Appendix 2. ECOG Status Scores

| Status | Eastern Cooperative Oncology Group (ECOG) Performance Status** |
|--------|---|
| 0 | Fully active, able to carry on all predisease performance without restriction. |
| 1 | Restricted in physically strenuous activity but ambulatory and able to carry out work of a light or sedentary nature, e.g., light housework, office work. |
| 2 | Ambulatory and capable of all self-care, but unable to carry out any work activities. Up and about more than 50% of waking hours. |
| 3 | Capable of only limited self-care, confined to bed or chair more than 50% of waking hours. |
| 4 | Completely disabled. Cannot carry on any self-care. Totally confined to bed or chair. |
| 5 | Dead. |

Available at: http://www.ecog.org/general/perf_stat.html. Accessed January 4, 2008.

Appendix 3. Inhibitors and Inducers of CYP3A

Inhibitors of CYP3A are defined as follows. A comprehensive list of inhibitors can be found at the following website: <http://medicine.iupui.edu/clinpharm/ddis/table.aspx>. The general categorization into strong, moderate, and weak inhibitors according to the website is displayed below. Refer to [Section 6.2.1](#) on instructions for concomitant use of CYP3A inhibitors and inducers with ibrutinib.

Source: <http://medicine.iupui.edu/clinpharm/ddis/table.aspx>.

| Inhibitors of CYP3A | Inducers of CYP3A |
|-------------------------------------|--------------------------|
| Strong inhibitors: | carbamazepine |
| indinavir | efavirenz |
| nelfinavir | nevirapine |
| ritonavir | barbiturates |
| clarithromycin | glucocorticoids |
| itraconazole | modafinil |
| ketoconazole | oxcarbazepine |
| nefazodone | phenobarbital |
| saquinavir | phenytoin |
| suboxone | pioglitazone |
| telithromycin | rifabutin |
| cobicistat | rifampin |
| boceprevir | St. John's Wort |
| mibefradil | troglitazone |
| telaprevir | |
| troleandomycin | |
| posaconazole | |
| Moderate inhibitors: | |
| aprepitant | |
| amprenavir | |
| amiodarone | |
| atazanavir | |
| ciprofloxacin | |
| crizotinib | |
| darunavir/ritonavir | |
| dronedarone | |
| erythromycin | |
| diltiazem | |
| fluconazole | |
| fosamprenavir | |
| grapefruit juice | |
| Seville orange juice | |
| verapamil | |
| voriconazole | |
| imatinib | |
| Weak inhibitors: | |
| cimetidine | |
| fluvoxamine | |
| All other inhibitors: | |
| chloramphenicol | |
| delaviridine | |
| diethyl-dithiocarbamate | |
| gestodene | |
| mifepristone | |

| | |
|---------------|--|
| norfloxacin | |
| norfluoxetine | |
| star fruit | |

Appendix 4. Child-Pugh Score

| Measure | 1 point | 2 points | 3 points |
|--|------------|--|------------------------------|
| Total bilirubin, $\mu\text{mol/L}$ (mg/dL) | <34 (<2) | 34-50 (2-3) | >50 (>3) |
| Serum albumin, g/L (g/dL) | >35 (>3.5) | 28-35 (2.8-3.5) | <28 (<2.8) |
| PT INR | <1.7 | 1.71-2.30 | >2.30 |
| Ascites | None | Mild | Moderate to Severe |
| Hepatic encephalopathy | None | Grade I-II (or suppressed with medication) | Grade III-IV (or refractory) |

| Points | Class |
|--------|-------|
| 5-6 | A |
| 7-9 | B |
| 10-15 | C |

Source:

Appendix 5. Patient Pill Diaries

Participant Dosing Diary and Instructions

Study IRB #161755 **Study site and ID # _____**
Cycle #: _____

Site Staff Instructions:

Please enter below the dates (mm/dd/yyyy) for the current cycle for Day 1-28.

| | Study Medication | | Daily Dose | Source |
|---|---|--|-----------------------|---------------|
| Day 1 - 28 Medications From: -- / / -- (MM / DD / YYYY) To: -- / / -- (MM / DD / YYYY) |  | 140 mg Ibrutinib x 4 capsules = 560 mg daily | 4 capsules | 140 mg bottle |

Participant Instructions:

- Swallow study drug whole and do not to chew or open them prior to swallowing.
- Take medication four capsules per day WITH 8 OZ OF WATER, at approximately the same time daily.
- If you miss a day's dose at the scheduled time, it can be taken as soon as possible on same day with a return to the normal schedule the following day.
- If you miss a day's dose entirely, you should NOT make it up the next day.
- If you vomit after taking a dose you should NOT make it up and should resume treatment the next day.
- If you inadvertently take 1 extra dose during a day, you should NOT take the next day's dose.
- Keep the medication in the bottles provided and do not transfer it to any other container.
- Record each dose of study medication in the diary section below. To prevent any dosage error, the participant diary should be completed every day.
- UNUSED DRUG and bottles should be RETURNED to the site at the next study visit.
- ALWAYS BRING your completed participant diary to the clinic at EACH study visit.
- Please avoid grapefruit and Seville oranges for the duration of the study.
- Please avoid using CYP3A inhibitors/inducers (e.g. indinavir, nefazodone)
- In case of any question, problem, or if you are not feeling well, please contact your study doctor.

| DAY | DATE (mm/dd/yy) | TIME Hour/Min (24:00 clock) | Number of Capsules TAKEN (Daily dose is 4 capsules, please add to the appropriate columns below; "4" if 4 pills were taken or "0" if no pills were taken) | COMMENT (e.g., Please use this section to write down any side effects you are experiencing on a given day, explanation for any extra doses taken or missed doses, etc.) |
|---|--------------------|-----------------------------------|---|---|
| | | | 140 mg = each pill | |
| 1 | | | | |
| The dose of Day 1 should be taken in the clinic according to site staff's instructions. Take Ibrutinib before Cetuximab infusion. | | | | |
| 2 | | | | |
| 3 | | | | |
| 4 | | | | |
| 5 | | | | |
| 6 | | | | |
| 7 | | | | |
| 8 | | | | |
| Take Ibrutinib before Cetuximab infusion. | | | | |
| 9 | | | | |
| 10 | | | | |
| 11 | | | | |
| 12 | | | | |
| 13 | | | | |
| 14 | | | | |
| 15 | | | | |
| Take Ibrutinib before Cetuximab infusion. | | | | |
| 16 | | | | |
| 17 | | | | |
| 18 | | | | |
| 19 | | | | |
| 20 | | | | |
| 21 | | | | |
| 22 | | | | |
| Take Ibrutinib before Cetuximab infusion. | | | | |
| 23 | | | | |
| 24 | | | | |
| 25 | | | | |

| | | | | |
|----|--|--|--|--|
| 26 | | | | |
| 27 | | | | |
| 28 | | | | |

Other Medications Taken

If you take a daily medication (prescribed or otherwise), please use one line per drug and indicate the start and stop dates under the “Dates Taken”

| Drug Name | Dose and Schedule | Dates Taken | Reasons Taken |
|-----------|-------------------|-------------|---------------|
| | | | |
| | | | |
| | | | |
| | | | |
| | | | |
| | | | |
| | | | |
| | | | |
| | | | |
| | | | |
| | | | |
| | | | |
| | | | |
| | | | |
| | | | |
| | | | |
| | | | |

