5.3.1.4. Dose Modification for Adverse Reactions

The dose of ibrutinib should be modified according to the dose modification guidelines in Table 1 if any of the following toxicities occur:

- Grade 4 ANC ($<500/\mu\text{L}$) for more than 7 days. See Section 6.1 for instructions regarding the use of growth factor support.
- Grade 3 thrombocytopenia ($<50,000/\mu\text{L}$) in the presence of clinically significant bleeding events.
- Grade 4 thrombocytopenia ($<25,000/\mu\text{L}$).
- Grade 3 or 4 nausea, vomiting, or diarrhea if persistent, despite optimal anti-emetic and/or anti-diarrheal therapy.
- Any other Grade 4 or unmanageable Grade 3 toxicity.

For Grade 3 or 4 atrial fibrillation or persistent atrial fibrillation of any grade, consider the risks and benefits of ibrutinib treatment. If clinically indicated, the use of anticoagulants or antiplatelet agents may be considered for the thromboprophylaxis of atrial fibrillation (See Section 6.2.4).

If the dose of ibrutinib is reduced, at the investigator's discretion, the dose of ibrutinib may be re-escalated after 2 cycles of a dose reduction in the absence of a recurrence of the toxicity that led to the reduction. Dose changes must be recorded in the Dose Administration eCRF.

Table 1. Ibrutinib Dose Modifications

| Occurrence | Action to be Taken |
|------------|---|
| First | Withhold study drug until recovery to Grade \leq 1 or baseline; may restart at original dose level |
| Second | Withhold study drug until recovery to Grade \leq 1 or baseline; may restart at 1 dose level lower (i.e., 280 mg/day for 420 mg/day dose; 420 mg/day for 560 mg /day dose) |
| Third | Withhold study drug until recovery to Grade \leq 1 or baseline; may restart at 1 dose level lower (i.e., 140 mg/day for 420 mg/day dose; 280 mg/day for 560 mg /day dose) |
| Fourth | Discontinue study drug |

Table 2. Ibrutinib Dose Reduction Levels

| Starting Dose Level | 560 mg |
|------------------------|-------------|
| Dose Reduction Level 1 | 420 mg |
| Dose Reduction Level 2 | 280 mg |
| Dose Reduction Level 3 | Discontinue |
| Dose Reduction Level 4 | NA |
| Dose Reduction Level 5 | NA |

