5.3.1.5. Dose Modification for Hepatic Impaired Subjects

Ibrutinib is metabolized in the liver and therefore subjects with clinically significant hepatic impairment at the time of screening (Child-Pugh class B or C) are excluded from study participation. Refer to Appendix 4 for Child-Pugh classification. For subjects with existing chronic mild hepatic impairment (Child-Pugh class A) at enrollment, the starting dose has to be adjusted to a level of 280 mg daily (two capsules). For subjects who develop mild liver impairment while on study (Child-Pugh class A), the recommended dose reduction for ibrutinib is to a level of 280 mg daily (two capsules) unless lower doses had already been implemented. For subjects who develop moderate liver impairment while on study (Child-Pugh class B), the recommended dose reduction is to a level of 140 mg daily (one capsule). Subjects who develop severe hepatic impairment (Child-Pugh class C) must hold study drug until resolved to moderate impairment (Child-Pugh class B) or better and could be re-treated according to resolved hepatic conditions (i.e., 140 mg or 280 mg for moderate or mild impairment, respectively). Subjects who develop acute hepatic toxicity with liver enzymes Grade 3 or higher while on study should be managed per standard dose modification guidelines in Section 5.3.1.4.

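### The Appendix 5 pill diary tells every participant to take four capsules (560 mg) a day and has no field for a reduced dose, contrary to the protocol's 420, 280 and 140 mg rules

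*Combined protocol and SAP*

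**What the plan says.** Appendix 5 is the only diary in the document. It states the dose in three places:

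- The medication table: "140 mg Ibrutinib x 4 capsules = 560 mg daily". Its daily-dose column is pre-printed with four capsules.
- The participant instruction: "Take medication four capsules per day WITH 8 OZ OF WATER, at approximately the same time daily".
- The header of the capsules-taken column: "Daily dose is 4 capsules, please add to the appropriate columns below". It then offers 4 or 0 as the entries.

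The direction to site staff is "Please enter below the dates (mm/dd/yyyy) for the current cycle for Day 1-28". The other blanks in the heading are for site, participant number and cycle.

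The protocol body sets 560 mg as the standard dose (Sections 3.2.2, 5.1.1 and 5.3.1.2) and then departs from it:

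- Section 5.3.1.4, Table 1: "420 mg/day for 560 mg /day dose" at the second occurrence of a qualifying toxicity, and "280 mg/day for 560 mg /day dose" at the third.
- Section 5.3.1.5, for Child-Pugh A at enrollment: "the starting dose has to be adjusted to a level of 280 mg daily (two capsules". The same level is recommended if class A develops on study. For class B developing on study, "the recommended dose reduction is to a level of 140 mg daily (one capsule".
- Section 6.2.1: 140 mg while a moderate CYP3A inhibitor must be used, and 140 mg or a short interruption with a strong one.

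**The concern.** The diary is the dosing sheet that the patient takes home, as well as a record. For anyone on a reduced dose, its printed instruction conflicts with the protocol and errs toward too much drug.

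The reductions exist for patients with recurrent toxicity, hepatic impairment or an interacting drug. Section 4.2 excludes only Child-Pugh B and C, so a class A patient can enroll and be given the wrong instruction from the first dose. Section 1.4.1 reports single-dose AUC 2.7-fold higher in class A and 8.2-fold higher in class B than with normal liver function, and Section 1.5.1.1 reports major hemorrhage with ibrutinib, sometimes fatal.

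What is at stake is participant safety and dose accountability. Sample size, power and type I error are not involved.

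**Working it through.** **Inputs.** Capsule strength is 140 mg (Section 5.3.1.1). The diary dose is 4 capsules (Appendix 5). Assigned doses come from Sections 5.3.1.4, 5.3.1.5 and 6.2.1, and AUC ratios from Section 1.4.1. The 140 mg shown in Table 1 is for a 420 mg starting dose, which this trial does not use, so the 140 mg rules here rest on Sections 5.3.1.5 and 6.2.1.

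**The diary's own figure.** 4 × 140 = 560 mg, which agrees with the standard dose.

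**Diary dose against assigned dose, per day.** Ratio = 560 / assigned; excess = 560 − assigned.

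| Assigned dose | Capsules | Ratio | Excess |
|---|---|---|---|
| 560 mg | 4 | 1 | 0 |
| 420 mg | 3 | 560/420 = 1.33 | 140 mg |
| 280 mg | 2 | 560/280 = 2 | 280 mg |
| 140 mg | 1 | 560/140 = 4 | 420 mg |

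**Exposure in hepatic impairment, relative to a normal-liver patient on 560 mg.** Relative exposure = AUC ratio × dose / 560. This assumes exposure proportional to dose, which Section 1.4.1 states only for 420 to 840 mg/day, and it applies single-dose ratios to daily dosing.

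- Child-Pugh A, assigned 280 mg: 2.7 × 280/560 = 1.35. On four capsules: 2.7 × 560/560 = 2.7.
- Child-Pugh B, assigned 140 mg: 8.2 × 140/560 = 2.05. On four capsules: 8.2 × 560/560 = 8.2.

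**Total over a cycle.** This depends on how many capsules are dispensed and how long the reduction lasts, and the documents give neither. Suppose exactly 28 days' supply is dispensed at the assigned dose. At four a day it would run out after 3 × 28 / 4 = 21 days, 2 × 28 / 4 = 14 days or 1 × 28 / 4 = 7 days. The cycle total would then be right, but taken too fast. If the dose is reduced mid-cycle while the patient still holds capsules dispensed for 560 mg, that supply limit does not apply.

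**Is the form adapted anywhere?** No section tells staff to amend or replace the diary when the dose changes. Section 5.3.1.4 sends the change to the dose administration eCRF, and Section 5.3.1.2 requires unused capsules back and accountability updated at each visit. Both record what happened, and neither changes what the patient reads.

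**The case against.** The best reply is that the diary restates the standard regimen and leaves out the exceptions, and that a clinician handles every exception in person. Cetuximab is infused weekly, so patients are in clinic often. The Day 1 dose is taken there under staff direction. Patients bring the diary to each visit and are told to call with questions. Under Table 1 a toxicity reduction follows a hold and a supervised restart. The capsules-taken cell is blank, so a patient can write 3, 2 or 1. The bottle label and pharmacy manual were not available and may carry the assigned dose.

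On size, four capsules after a toxicity reduction only returns the patient to the starting dose, to which Section 5.3.1.4 itself allows re-escalation after two cycles without recurrence. Section 5.3.1.3 reports no maximum tolerated dose up to 1400 mg/day. The 8.2-fold figure needs a patient who becomes Child-Pugh B on study and then follows the form over the physician's advice.

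Much of this stands as a limit on the likely harm. The form is right for patients on 560 mg, few may be on a reduced dose, and the class B case is the extreme one. But none of it corrects the printed instruction. The documents do not say that diaries or capsules are checked at weekly infusions, and cetuximab may be held while ibrutinib continues. A correct label would leave the patient with two conflicting instructions. The points about toxicity reductions do not cover hepatic impairment or CYP3A inhibitors.

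**Conclusion.** The concern holds. For any patient not on 560 mg, the diary gives an instruction that conflicts with the protocol and would deliver 1.33, 2 or 4 times the assigned daily dose if followed. The contradiction and these ratios follow directly from the text.

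The exposure figures (about 2.7 rather than 1.35 in Child-Pugh A, and 8.2 rather than 2.05 in Child-Pugh B) rest on single-dose AUC ratios and on proportionality outside its stated range, so they are indicative only. How many of the 18 patients would be on a reduced dose, and how many would follow the form over verbal or label instructions, cannot be known from the documents.

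This should be corrected on safety grounds. It does not bear on the primary response-rate analysis.

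**What to change.** In Appendix 5, remove the fixed four-capsule wording from the medication table, the participant instruction and the log header, along with the 4-or-0 coding. Put in a capsules-per-day field that site staff complete at each dispensing and at every dose change, and ask the patient to enter the number actually taken.

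In the same revision, add seven lines (Days −7 to −1) to the cycle 1 sheet. Appendix 1 makes cycle 1 35 days long because ibrutinib starts a week before cetuximab, but the diary has lines only for Days 1 to 28. That is a recording gap and alters no dose or analysis.

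The cost is one revised form. As the form is a protocol appendix, the Section 14.8 steps apply: review and approval by the ibrutinib supplier, then the IRB at each site and submission to FDA. Dosing rules, sample size and analysis stay as they are.
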